***INTRA-CELLULAR THERAPIES INC. (ITCI)***

STATISTICAL ANALYSIS PLAN: PROTOCOL ITI-007-401

Page 53 of 70

[figure not shown]
---

***INTRA-CELLULAR THERAPIES INC. (ITCI)***

STATISTICAL ANALYSIS PLAN: PROTOCOL ITI-007-401

Page 54 of 70

---

[figure not shown]

***INTRA-CELLULAR THERAPIES INC. (ITCI)***

STATISTICAL ANALYSIS PLAN: PROTOCOL ITI-007-401

Page 55 of 70

---

## APPENDIX 2. PARTIAL DATE CONVENTIONS

Imputed dates will NOT be presented in the listings.

### ALGORITHM FOR TREATMENT EMERGENCE OF ADVERSE EVENTS

START DATE	STOP DATE	ACTION
Known	Known	
If start date < study medication start date or start date>study medication end date + 1 day , then not TEAE
 
If study medication start date ≤ start date ≤ study medication end date + 1 day, then TEAE

	Partial	
Impute stop date as latest possible date (i.e. last day of month if day unknown or 31st December if day and month are unknown), then:
 
If start date < study med start date or start date>study med end date + 1 day, then not TEAE
 
If study med start date ≤ start date ≤ study med end date + 1 day, then TEAE

	Missing	
If start date < study med start date or start date>study med end date + 1 day, then not TEAE
 
If study med start date ≤ start date ≤ study med end date + 1 day, then TEAE

Partial, but known components show that it cannot be on or after study medication start date or cannot be before study medication end date	Known	Not TEAE
	Partial	Not TEAE

START DATE	STOP DATE	ACTION
	Missing	Not TEAE
Partial, could be on or after study medication start date but before study med end date	Known	If stop date < study med start date, then not TEAE If stop date $\geq$ study med start date, then TEAE
	Partial	Impute stop date as latest possible date (i.e. last day of month if day unknown or 31st December if day and month are unknown), then: If stop date < study med start date, then not TEAE If stop date $\geq$ study med start date, then TEAE
	Missing	Assumed TEAE
Missing	Known	If stop date < study med start date, then not TEAE If stop date $\geq$ study med start date, then TEAE
	Partial	Impute stop date as latest possible date (i.e. last day of month if day unknown or 31st December if day and month are unknown), then: If stop date < study med start date, then not TEAE If stop date $\geq$ study med start date, then TEAE
	Missing	Assumed TEAE

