### **16.1. ADVERSE EVENTS**

Adverse Events (AEs) will be coded using MedDRA central coding dictionary currently in effect at the time of interim analysis or final Part A database lock.

Treatment emergent adverse events (TEAEs) are defined as AEs that started or worsened in severity on or after the date of the first dose of study medication and on or before the date of last dose of study medication in Part A plus one day.

All AEs with an onset date after the last dose of study medication plus one day, but before the start of Part B will be listed in the AE data listing and labelled as 'Follow-up Adverse Event'.

See [Appendix 2](#) for handling of partial or completely missing dates for AEs. In the case where it is not possible to define an AE as treatment emergent or not, the AE will be classified as the worst case, i.e., treatment emergent.

An overall summary of the number of subjects within each of the categories described in the [sub-sections 16.1.1](#) and [16.1.2](#) below will be provided as specified in the TLF shells.

Listings will include all adverse events, TEAEs and Non-TEAEs.

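### The partial-onset rows of SAP Appendix 2 omit the extra day of the TEAE window, so an adverse event that may lie inside the window is classed as not treatment-emergent

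*SAP*

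**What the plan says.** SAP 16.1 counts an event as a TEAE if it starts or worsens from the first-dose date onward, provided this happens "on or before the date of last dose of study medication in Part A plus one day". It refers partial and missing dates to Appendix 2 and adds that "where it is not possible to define an AE as treatment emergent or not, the AE will be classified as the worst case", meaning treatment-emergent.

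The algorithm for treatment emergence in Appendix 2 then works by type of onset date:

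- **Known onset:** "If study medication start date ≤ start date ≤ study medication end date + 1 day, then TEAE". The same limit is used whether the stop date is known, partial or missing.
- **Partial onset, first row:** if the known components show that the onset "cannot be on or after study medication start date or cannot be before study medication end date", the result is Not TEAE for every type of stop date.
- **Partial onset, second row:** the condition is "Partial, could be on or after study medication start date but before study med end date". Only events that meet it can become TEAEs, depending on the stop date.
- **Missing onset:** TEAE unless the stop date precedes the first dose. If the stop date is missing too, the event is assumed to be a TEAE.

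**The concern.** The known-onset rows close the window at last dose plus one day. The partial-onset rows close it before the last-dose date. Two days that the SAP counts as treatment-emergent, the last-dose day and the day after, are thus lost whenever the onset is partial and no earlier date is possible.

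The error runs in the anti-conservative direction, because a possible TEAE is removed. It also reverses the SAP's own principle: when the stop date is missing, an event with no onset date at all becomes a TEAE, while an event known to have started in the month that begins on the last-dose date does not.

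A misfiled event would leave the TEAE incidence, 5% threshold and relative-risk summaries of SAP 16.1.1, and the extrapyramidal and abuse-related summaries of 16.1.3 and 16.1.4 where it carries a relevant term.

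**Working it through.** The plan gives no figure to reproduce, so the check compares the two rules date by date.

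**Rules, from SAP 16.1 and Appendix 2**

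- Window: first dose ≤ onset ≤ last dose + 1 day.
- First partial row: Not TEAE if the latest possible onset is before first dose, or the earliest possible onset is on or after last dose.

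The first limb agrees with the window. The second does not.

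**Onset month and year known, day missing**

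| Last dose | Recorded onset | Earliest possible onset | Appendix 2 result | Possible dates inside the window |
|---|---|---|---|---|
| 1 March | March | 1 March = last dose | Not TEAE | 1 and 2 March |
| 28 February (non-leap year) | March | 1 March = last dose + 1 | Not TEAE | 1 March |
| 31 January | February | 1 February = last dose + 1 | Not TEAE | 1 February |

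For any other last-dose date, the current month starts before the last dose, so the event goes to the second partial row. The next month starts at least two days after the last dose, outside the window. The exposed dates are therefore the first and last day of each month: 12 × 2 = 24, and 24/365 = 6.6%. Running every last-dose date in 2018 and in 2019, with 42 days of dosing assumed, gives 24 of 365 in each year. If only the onset year is known, the exposed last-dose dates are 31 December and 1 January.

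**The stop date does not help.** Take the third example with a known stop date of 1 February. The onset cannot follow the stop, so it must be 1 February, which is last dose + 1 day. That is a certain TEAE under 16.1, and the row still returns Not TEAE.

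**Expected number of events.** The documents give neither an adverse event count nor a partial-date rate. Assumptions:

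- 800 to 1,500 adverse events, of which 1% to 3% have a partial onset. This gives 800 × 0.01 = 8 to 1,500 × 0.03 = 45 partial-onset events.
- Last dose on Day 42, onsets uniform over Days 1 to 57, last-dose dates spread evenly over the year, and only the onset day missing.

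For a last dose on the last day of a month, 15 onset days (Days 43 to 57) carry the exposed month. For a last dose on the first day, 16 do (Days 42 to 57).

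- Filed as Not TEAE although possibly in the window: (12 × 15 + 12 × 16)/(365 × 57) = 372/20,805 = 1.8%. Applied to 8 to 45 events, this is about 0.14 to 0.8.
- Truly in the window and misfiled (one possible day for a last-day dose, two for a first-day dose): (12 × 1 + 12 × 2)/(365 × 57) = 36/20,805 = 0.17%, or about 0.01 to 0.08 events.

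**After correction.** If Not TEAE requires the earliest possible onset to be later than last dose + 1 day, the exposed last-dose dates fall from 24 to 0.

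**The case against.** The best defence is that SAP 16.1 already states the intended result. The examples are cases where emergence cannot be determined, and "the AE will be classified as the worst case, i.e., treatment emergent". On that reading this is a drafting slip that a careful programmer would resolve correctly. That holds as a statement of intent but does not repair the rule: 16.1 refers partial dates to Appendix 2, which gives a definite answer, so anyone coding the table never reaches the fallback.

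The second defence is that little is lost, and most of it stands. Events with complete dates are handled correctly. The listings contain both TEAEs and non-TEAEs, and the SAE and discontinuation summaries are not described as limited to TEAEs. Adverse events in the follow-up period are also summarised, and the rule is the same in every arm.

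Three stronger readings are tempting, and the documents do not support them:

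- **That 6.6% of patients are affected.** The 24 of 365 is a share of calendar dates. A patient is affected only if the last dose falls on such a date, an adverse event has a partial onset, and its recorded month is the one starting there.
- **That 0.5 to 3 events are affected.** This comes from multiplying 8 to 45 partial-onset events by 6.6%. It ignores the matching-month condition and so counts events from earlier weeks of treatment that the row does not touch.
- **That the 14-day limit in Protocol 7.5.8 enlarges the problem.** The SAP does not use that window. The difference between the two documents is a separate question, and this point rests on the SAP's own limit.

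**Conclusion.** The point holds as an internal inconsistency in the SAP. The partial-onset rows contradict both the TEAE definition and the worst-case rule in 16.1, and can exclude even a certain TEAE. The visible text settles this; no redacted section is needed.

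The size is small. Under the stated assumptions fewer than one event would be misfiled, and fewer than 0.1 would truly lie in the window. These counts rest on an assumed number of events, an assumed partial-date rate and uniform onset; the 24 calendar dates need none of these. The inconsistency is very unlikely to change any safety conclusion. It is worth correcting because one algorithm should apply one window, and because the error runs against the SAP's declared conservatism.

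**What to change.** In the treatment-emergence table of SAP Appendix 2:

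- First partial-onset row: keep the limb on the start date and change the second limb to *cannot be on or before study medication end date + 1 day*.
- Second partial-onset row: change the closing condition to *and on or before study medication end date + 1 day*.

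The cost is two phrases and one line of the derivation.

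There is one side effect. For direct rollovers, Protocol 5.1 makes Day 43 the first day of Part B, about one day after the last Part A dose. With a last Part A dose on 28 February and onset recorded as March, the revised row would count the event as a Part A TEAE although only 1 March, one of 31 possible dates, is inside the Part A window. That is consistent with the worst-case rule. A short note should say that the event is not counted in Part A when known date components or other records place its onset after the start of Part B.

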## ALGORITHM FOR PRIOR / CONCOMITANT MEDICATIONS

START DATE	STOP DATE	ACTION
Known	Known	
If stop date < study med start date, assign as prior
 
If stop date <math>\geq</math> study med start date and start date < study med start date, assign as prior concomitant
 
If stop date <math>\geq</math> study med start date and start date <math>\leq</math> end of treatment, assign as concomitant
 
If stop date <math>\geq</math> study med start date and start date <math>></math> end of treatment, assign as post study

	Partial	
Impute stop date as latest possible date (i.e. last day of month if day unknown or 31st December if day and month are unknown), then:
 
If stop date < study med start date, assign as prior
 
If stop date <math>\geq</math> study med start date and start date < study med start date, assign as prior concomitant
 
If stop date <math>\geq</math> study med start date and start date <math>\leq</math> end of treatment, assign as concomitant
 
If stop date <math>\geq</math> study med start date and start date <math>></math> end of treatment, assign as post study

	Missing	
If stop date is missing could never be assumed a prior medication
 
If start date <math>\leq</math> end of treatment, assign as concomitant
 
If start date <math>></math> end of treatment, assign as post treatment

Partial	Known	
Impute start date as earliest possible date (i.e. first day of month if day unknown or 1st January if day and month are unknown), then:
 
If stop date < study med start date, assign as prior
 
If stop date <math>\geq</math> study med start date and start date < study med start date, assign as prior concomitant
 
If stop date <math>\geq</math> study med start date and start date <math>\leq</math> end of treatment, assign as concomitant
 
If stop date <math>\geq</math> study med start date and start date <math>></math> end of treatment, assign as post study

START DATE	STOP DATE	ACTION

100% of the time, the system is able to correctly identify the target class. This is a significant improvement over the baseline model, which only achieves 50% accuracy. The results are summarized in the following table:

Page 1 of 1

For more information, contact the Office of the Vice President for Research and Economic Development at [contact] or [[contact]](mailto:[contact]).

The figure consists of a 10x2 grid of horizontal bars. The left column contains 10 bars, each divided into two segments: a shorter black segment on the left and a longer white segment on the right. The right column contains 10 bars, each divided into two segments: a longer black segment on the left and a shorter white segment on the right. The bars are arranged in a staggered pattern, with the first bar of the left column aligned with the second bar of the right column, and so on.

1. **What is the primary purpose of the proposed legislation?**

[REDACTED]

[REDACTED]  $\sqrt{[REDACTED]}$  [REDACTED]

[REDACTED]
